A new group of intensivists, oncologists, emergency medicine physicians and hospitalists will be recruited including resident and fellow trainees in those specialties. Physician subjects will be recruited face-to-face by the PI, through departmental email blasts and emails to contacts of the study team. As in phase 1, physicians will complete a screening questionnaire to exclude those that do not routinely encounter hospitalized patients with a life expectancy of less than one year. Potential subjects will be asked about the frequency and timing of previous communication and bias training. Physicians practicing Hospice and Palliative Medicine will be excluded because of their extensive prior training in communication.

Data collection:

Encounters will be videotaped. We will use the five-point verbal communication rating scale and nonverbal communication behaviors coded with the NAAS during the standardized encounter as described in phase 1 above.^{111,114} A research assistant who did not participate in the training sessions and is blinded to participant group will code communication behaviors. Subjects will complete the IAT and the questionnaire described in phase 1 immediately after the first encounter.

Outcome measures:

Subjects will complete an on-line questionnaire at the close of the session with Likert-type questions on the usefulness and acceptability of the training program and self-efficacy with cross-cultural communication. In addition, the questionnaire will include the cognitive and affective empathy portions of the Interpersonal Reactivity Index. For participants in the active group only, several questions will assess the illusion of ownership of the virtual body in the VR experience. An open-ended text box will invite feedback. The primary efficacy endpoint will be verbal dominance (ratio of clinician to patient speaking time during the encounter with a ratio of >1 meaning that the clinician dominated the discussion).⁹⁹ Secondary endpoints will include

Protocol #

verbal and nonverbal communication and encounter duration. Inter-rater reliability for the communication scores will be reported using Kappa values.

Analysis plan:

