Initially, the mean change in verbal and nonverbal communication scores pre- and post-intervention will be evaluated within each intervention arm using paired *t*-tests or Wilcoxon tests if the data are not normally distributed. To assess whether communication scores improved more in the bias mitigation treatment compared with communication training only control, a generalized linear model will be fit to the data with post-intervention score as the outcome, and pre-intervention score and intervention arm as the main effects. In addition, we will investigate whether pre-intervention level of bias modifies the effect of bias mitigation training, e.g., those with more bias will have a greater difference in improvement between the intervention and control group, by including in the model an interaction term between IAT score and treatment group on communication scores. A positive interaction will indicate that implicit bias as measured by the IAT modifies the effect of treatment group on communication score. With 25 subjects per intervention arm, the study will have 80% power to detect an effect size of 0.8 between groups in pre-post change in communication scores with a two-sided Type 1 error rate of 5%. While this is considered a large effect size according to Cohen's criteria, we would like emphasize that this is a pilot study in which the primary goal is to assess feasibility and to generate preliminary data on the effect of the proposed communication training intervention for clinicians to mitigate the effects of implicit bias.

$\Delta y = \alpha + \beta_0(Tx) + \beta_1(IAT) + \beta_2(Tx \times IAT) + \epsilon_1$, where Δy = change in communication score, Tx = treatment group

Data Management/Analysis:

Protocol #

Communication behavior codes and data from the questionnaires and IAT stored on Montefiore's secure Box drive and will only be accessible by members of the research team. Video recordings will be stored on a password-protected hard drive accessible only to the research team.

Risks/Benefits:

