Potential risks: This research poses two main risks to subjects: 1) emotional distress and 2) risk to privacy. There may be some emotional distress caused by learning about one's unconscious racial biases. Emotional distress may also result from passive deception; subjects will not be told that racial bias is the focus of the study until after the intervention. Privacy risk arises because racial biases may be considered sensitive information about the subject.

Adequacy of Protection Against Risks

Recruitment and Informed Consent: All subjects will be recruited by the PI through departmental email blasts, emails to contacts of the study team and departmental faculty meeting presentations. The consent process will take place in the Clinical Skills Center on the prior to the standardized patient encounter. Subjects will be informed of their right to participate or discontinue participation at any time without jeopardizing their employment, professional position or relationships with colleagues. Copies of the signed consent form will be given to the subject and placed in the subject's research folder in a locked file drawer in an office in the PI's office expressly designed for this purpose.

Incomplete disclosure of information during the consenting process: Subjects will be informed that they are participating in a study exploring physician cognition, cognitive biases and communication behavior. They will be informed that study participation includes completion

Protocol #

of an on-line instrument after the standardized patient encounter. They will not be told during the consent process that implicit racial bias and stereotyping are the focus of the study.

Incentives: Incentives have been chosen to provide a counterbalance to the opportunity costs of participating by offering continuing medical education (CME) credits for attending physician participants. Given that CME credits can be obtained in many ways, this incentive is not to be enough to be coercive. Since resident and fellow participants are unable to use CME credits during training, they will be offered a \$50 gift card to compensate them for their time.

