Protections against risks: Personal identifiers not be collected in the on-line instrument; instead a unique study ID will be assigned to each participant. Video recordings will be maintained in a password protected digital folder on a hard drive in a locked office. This database of coded communication scores will be stripped of participant identifiers as soon as all data is collected, and a file linking the study ID and patient identifiers will be kept in a separate, password protected digital folder.

Debriefing: After completion of the on-line bias measurement instrument, the subjects will be shown a debriefing statement including full disclosure of the aims of the study and the intent to examine the relationship between implicit racial bias and stereotyping and communication behavior. This statement will include a reminder that they may discontinue participation at any time and request that their data be removed from the dataset without penalty. The PIs contact information will be provided.

Potential Benefits of the Proposed Research: Subjects are not expected to directly benefit from this research.

[figure not shown]
Importance of the knowledge to be gained: The information from this study will provide knowledge about the role of implicit bias and stereotyping in communication behaviors that have

Protocol #

profound effects on the quality of end of life care for black patients. It will also inform efforts to mitigate the effects of this bias in future studies.

Necessity of withholding information in the consent process: Withholding of complete information from the consent process is only acceptable if there is no reasonably effective alternative to achieve the goals of the research. In this case, knowledge of the intent to study implicit racial bias is likely to affect the way physicians communicate in the standardized patient encounter, thus invalidating the results of the study.

Figures:

References:

1. Chartbook on Health Care for Blacks. Part 1: Overviews of the Report and the Black Population. Agency for Healthcare Research and Quality, 2015. (Accessed June 21, 2019, 2019, at <https://www.ahrq.gov/research/findings/nhqrdr/chartbooks/blackhealth/part1.html>.)

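### Asking about past bias training, apparently at screening, is an avoidable partial cue to the concealed topic before the first encounter; it should move to the questionnaire completed with the IAT

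*Combined protocol and SAP*

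**What the plan says.** The same sentence appears under Study population in Phase 1 and under Study population and Recruitment in Phase 2: "Potential subjects will be asked about the frequency and timing of previous communication and bias training". In each place it follows the screening step, which Phase 2 describes thus: "As in phase 1, physicians will complete a screening questionnaire to exclude those that do not routinely encounter hospitalized patients". The exclusion of Hospice and Palliative Medicine physicians comes next.

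The section on incomplete disclosure sets out what candidates learn at consent: "Subjects will be informed that they are participating in a study exploring physician cognition, cognitive biases and communication behavior". It also sets out what is withheld: "They will not be told during the consent process that implicit racial bias and stereotyping are the focus of the study". The section on the necessity of withholding information gives the reason: "knowledge of the intent to study implicit racial bias is likely to affect the way physicians communicate in the standardized patient encounter". It adds that this would invalidate the results.

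The order of the other bias measures follows from that reason. In Phase 1 the IAT and the questionnaire on race and end-of-life attitudes come immediately after the simulation. For Phase 2, Data collection says: "Subjects will complete the IAT and the questionnaire described in phase 1 immediately after the first encounter". The Debriefing section puts full disclosure after the bias instrument.

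**The concern.** The plan relies on physicians not knowing, when they enter the first encounter, that racial bias is being studied. A candidate who has been asked about bias training, then told that the study concerns cognitive biases and communication, and then meets a Black caregiver has more to go on than one who was never asked. Some may guess the topic and monitor themselves.

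The first encounter supplies the Phase 1 primary endpoint and the Phase 2 pre-training score. If self-monitoring flattens the behaviour that the IAT is meant to predict, the Phase 1 association between IAT score and verbal dominance is attenuated. In Phase 2 the baseline could move and leave less room for improvement. The plan describes no filler items to mask the question and no check on whether subjects guessed the purpose, so a failure of concealment would go unseen.

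**Working it through.** The point concerns the order of procedures, so the check is mainly a comparison of sections.

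**1. When is the question asked?** It is put to potential subjects, and it stands between two screening rules. The consent process takes place at the Clinical Skills Center before the encounter. The likelier reading is therefore that the question precedes consent and the first encounter. This is inferred from wording and position; no section says outright that the item is in the screening questionnaire.

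**2. Does anything need the answer then?**
- Eligibility: the stated exclusions are not routinely seeing hospitalized patients with a life expectancy under one year, and practising Hospice and Palliative Medicine. Prior bias training is not among them.
- Randomization (Phase 2 Design): mixed blocks of 2, 4 and 6, with no stratification factor.
- Phase 1 model: the named confounders are age, gender and specialty. The list is open-ended, so training history could be added, but that would not require asking before the encounter.
- Phase 2 models: pre-intervention score, arm, IAT score and the interaction of arm with IAT score.

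No stated use depends on early collection.

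**3. How does it compare with the other bias measures?** The IAT, the attitude questionnaire and the debriefing all follow the first encounter. This item is the exception.

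**4. Which analyses can it touch?**
- Phase 1: the correlation and regression of verbal dominance on IAT score use first-encounter behaviour directly.
- Phase 2: candidates for both arms get the same question before any training, so it does not by itself create a difference between arms. It can shift the pre-training score in both.

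**5. Is there a size?** The documents give none. For context, the plan's own power figures are as follows.
- Phase 1: n = 50, rho = 0.38, two-sided 0.05. Fisher z power = Φ(atanh(0.38) × √47 − 1.96) = Φ(2.743 − 1.960) = 78.3%, or 79.1% with the bias correction. The plan says above 80%.
- Phase 2: 25 per arm, effect size 0.8. Power is 80.7% by the normal approximation and 79.1% by the noncentral t. The stated 80% is reproduced.

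To show sensitivity only, assume that a fraction f of physicians self-monitor so fully that they show no IAT association, with equal variances in both groups. The correlation is then (1 − f) × 0.38.

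| f (assumed) | correlation | Phase 1 power |
|---|---|---|
| 0% | 0.380 | 78% |
| 5% | 0.361 | 74% |
| 10% | 0.342 | 69% |
| 30% | 0.266 | 46% |
| 50% | 0.190 | 26% |

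Nothing in the documents says which row applies. The model also charges all self-monitoring to this one item, although the consent wording and the caregiver's race would remain after any fix.

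**The case against.** The best defence is that the item adds little. It does not mention race, its exact wording is not given, and consent already tells every subject that cognitive biases and communication are under study. A question on communication training and bias training fits that cover story. This stands in part: the item is a cue, and what it adds beyond the consent text is unmeasured. What remains is that the consent text places bias within physician cognition, whereas pairing bias training with communication training points towards bias between people.

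Four stronger readings are tempting, and the documents support none of them.

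- A reader might infer that the protocol itself says this question would invalidate the results. It does not. Its statement is about knowing the intent to study implicit racial bias, and being asked about past training is not the same thing.
- A reader might take the lower rows of the table as the expected loss of power. They follow from an assumed f and are not estimates.
- A reader might infer that the Phase 2 arm comparison is biased. The question is common to both arms, and the main model adjusts for the pre-intervention score. Phase 2 is also described as a pilot aimed chiefly at feasibility.
- A reader might suppose that recently trained physicians are the likeliest to notice the cue. That is plausible, but nothing in the documents bears on it.

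**Conclusion.** The concern holds as a point about ordering. In both phases an item that serves no stated purpose before the first encounter apparently precedes it, and it hints at the topic that the rest of the protocol keeps until afterwards. The consequence to guard against is attenuation of the Phase 1 association between IAT score and verbal dominance, in a phase whose recomputed power (78% to 79%) leaves no margin. In Phase 2 the effect is limited to a possible shift in baseline behaviour.

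The size of both effects is unknown. The conclusion rests on two assumptions: that the question is asked before the encounter, as its wording and position suggest, and that some physicians would connect it with the caregiver's race. It is not a contradiction in the protocol and does not show that the results would be invalid. The case for acting is that the change is nearly free and protects the premise on which the incomplete disclosure is justified.

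**What to change.** Remove the bias-training item from screening in both phases and add it to the existing questionnaire completed with the IAT immediately after the first encounter. In Phase 2 it must be completed before any training starts. Keep the item on communication training at screening. State in both Study population sections when each item is asked.

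Do not move the item to the questionnaire at the close of the Phase 2 session. By then one arm has had bias-mitigation training and the other has not, so recall and reporting of earlier bias training could differ by arm. Because the allocation envelope is opened after consent, the relocated item may no longer be strictly pre-randomization. It would still precede any difference in what the arms receive.

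If a check on concealment is wanted, ask one open question about the perceived purpose of the study right after the first encounter, before the IAT and the debriefing, and report it descriptively. Do not exclude subjects on a guess collected at the end: after the IAT, debriefing and training the answer is coloured by hindsight, and in Phase 2 the exclusion would be post-randomization selection from about 50 subjects.

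The cost is a minor IRB amendment and one relocated item, with no extra visits, staff or subjects.

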The aim of this study is to assess the effects of clinician racial bias on end-of-life communication and to develop interventions to reduce the effects of implicit bias on quality of clinician communication. There are two study objectives: (1) Establish which communication behaviors in the end-of-life setting are most affected by clinician implicit racial bias and explicit stereotyping. (2) Pilot a theory-driven intervention to improve clinician communication and reduce disparities in quality end-of-life care. These objectives will be met in two study phases.

Methods/Design:**Phase 1:****Methods:**

(1) I will develop a case depicting a hospitalized 72-year-old with lung cancer and sepsis due to pneumonia on high-flow nasal cannula with my mentorship team of experts in palliative medicine and critical care. I will design a clinical encounter with the caregiver to discuss goals of

Protocol #

care. 2) The caregiver encounter will be piloted with critical care and hospitalist physicians at Montefiore to ensure realism and achieve standardization.¹⁰⁸ Black standardized caregivers will be recruited from the pool of actors used by the Einstein Clinical Skills Center. (3) Standardized caregivers will be trained in the use of a communication assessment tool.¹⁰⁹ (4) 50 physicians will be recruited to participate in a videotaped high-fidelity simulation of the encounter. The session will be followed by a 1-hour communication skills training to allow participants to earn continuing medical education (CME) credit. (5) Immediately after the simulation subjects will complete the IAT and a questionnaire probing for attitudes about race and end-of-life care along with demographic questions. We will assess training needs by adapting a previously developed questionnaire measuring physicians' self-identified serious illness communication training needs by incorporating questions about bias mitigation skills.¹¹⁰ The IAT is publicly available here: <https://implicit.harvard.edu/implicit/selectatest.html>.

COVID-19 Concerns:

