This is a communication training session based on a culturally-based program developed with rural, southern Black patients and families by [name] and modified for an urban, northern population. A strategy of bias mitigation successfully used with medical students will be adapted for practicing clinicians using results of phase 1. This strategy is based on transformative learning theory and incorporates critical reflection, guided dialogue, perspective taking exercises, role plays and strategy development.¹⁰⁷ In this study, a virtual reality (VR) experience (<https://michigan.it.umich.edu/news/2023/07/31/education-and-awareness-in-vr-new-experience-illustrates-the-effects-of-racial-discrimination/>) will be used as the disorienting dilemma to spark the process of transformative learning. This brief experience embodies the participant in the experiences of an African American man over his life course. It is aimed to engender empathy and perspective taking. Following the VR experience, participants will debrief with the facilitator in small groups, discuss how implicit bias impacts the clinical encounter, brainstorm bias mitigation techniques and role-play strategies to mitigate bias in the clinical encounter. If specific communication behaviors are found related to bias and stereotyping in phase 1, these will be discussed and targeted using these techniques. Otherwise, these techniques will be used to address racial bias generally. The intervention will be incorporated within the communication training session.

Design:

Clinicians will be randomized 1:1 to the active intervention or a

control communication training without bias mitigation techniques. Allocation concealment will be in place to ensure the individual enrolling the subject into the study has no a priori knowledge

Protocol #

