of group assignment. Block randomization will occur with randomly mixed block sizes of 2, 4, and 6. The allocator (research assistant) will hide block size from the executor (PI) in order to prevent the executor from predicting the next assignment. Randomization will be carried out by having a piece of paper that has the phrase “Intervention (Communication + Bias)” or “Control (Communication only)” placed inside an opaque envelope. The outside of the envelopes will be labeled with the sequence number. After a subject has been enrolled into the study and consented, the next sequence numbered envelope on the stack will be opened to determine the study group that the subject will enter.

Participants will be videotaped during high-fidelity simulations of encounters with caregivers described in phase 1, before and after receiving the intervention or control. The intervention and simulations will take place in one half-day workshop.

COVID-19 Concerns:

The Clinical Skills Center will be holding in-person simulations with standardized patients for the purposes of medical education starting in May 2021. The simulations in this study will not begin until after that time and will involve less risk than typical simulations because they will not entail a physical examination of the standardized caregiver. Actors and participants will be equipped with personal protective equipment including surgical masks. Trainers and participants in the training session will be required to wear provided surgical masks and remain six feet apart during the training sessions. If COVID-19 state or institutional guidelines prohibit these types of encounters at the time the simulations will be launched, the simulations and training will be adapted to a virtual format and nonverbal behavior coding will be adjusted. These changes will be submitted to the IRB as an amendment.

Study population and Recruitment:

Protocol #

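### Phase 2 gives two unreconciled times for disclosing the racial-bias focus, and neither requires waiting until the second encounter, so controls may be told before the primary endpoint is measured

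*Combined protocol and SAP*

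**What the plan says.** **Sequence.** Under Phase 2, Design, participants are recorded in simulated encounters "before and after receiving the intervention or control. The intervention and simulations will take place in one half-day workshop". Under Phase 2, Data collection, "Subjects will complete the IAT and the questionnaire described in phase 1 immediately after the first encounter". The Phase 1 Methods describe that step: "Immediately after the simulation subjects will complete the IAT and a questionnaire probing for attitudes about race and end-of-life care". Under Phase 2, Outcome measures, "Subjects will complete an on-line questionnaire at the close of the session".

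**Arms.** In the active arm, participants "discuss how implicit bias impacts the clinical encounter, brainstorm bias mitigation techniques" after the virtual reality experience. The comparator is a "control communication training without bias mitigation techniques". The Analysis plan asks whether "communication scores improved more in the bias mitigation treatment compared with communication training only control".

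**Disclosure.** Three paragraphs under Risks/Benefits bear on timing.
- Potential risks: subjects do not learn that racial bias is the focus before the intervention is over.
- Debriefing: the statement of the full aims follows completion of the online bias instrument. It also reminds subjects that they may stop and have their data removed.
- Necessity of withholding information: knowing the focus is likely to change how physicians communicate in the encounter and so make the results invalid.

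None of the three distinguishes Phase 1 from Phase 2, or one arm from the other.

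**The concern.** The disclosure text appears to have been written for Phase 1, where there is one encounter and the bias instrument comes after it. The consent paragraph on incomplete disclosure likewise refers to a single encounter followed by an online instrument. In that design, a debriefing after the instrument cannot affect the recorded behaviour.

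Phase 2 has a second encounter after the instrument, and its communication scores are the outcome in the between-arm model. If controls are told the focus before it, they have received communication training plus disclosure, which is not the condition the Design and Analysis plan describe. The contrast between arms might then be attenuated, and the control arm's paired pre-post change would mix training with disclosure. A pilot meant to supply preliminary effect data should be clear about what its control arm received.

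**Working it through.** This is a check of wording and order.

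**1. Order of events in Phase 2** (Design, Data collection, Outcome measures): encounter 1; IAT and race-attitudes questionnaire; training (active or control); encounter 2; closing questionnaire. The closing questionnaire is taken as last because it is given at the close of the session.

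**2. The two disclosure statements against that order.**

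| Time of debriefing | Debriefing paragraph (after the instrument) | Potential risks paragraph (not before the intervention is over) | Encounter 2 still ahead? |
|---|---|---|---|
| Between IAT and training | Allowed; the natural reading | Not allowed | Yes |
| Between training and encounter 2 | Allowed | Allowed | Yes |
| After encounter 2 | Allowed | Allowed | No |

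The first row is where the paragraphs conflict, if the debriefing is read as following directly on the instrument. The second row shows that complying with both still leaves encounter 2 unprotected. The third row shows that a time satisfying both and protecting encounter 2 exists, but no passage selects it.

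**3. Against the protocol's own rationale.** The reason given for withholding is that knowledge of the focus changes behaviour in the encounter. It is offered as a justification for incomplete consent, and it does not set a debriefing time. The same reasoning applies to encounter 2, because the Phase 2 model takes the post-intervention score as outcome and the pre-intervention score as covariate.

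**4. The plan's figure.** The Analysis plan states 80% power for an effect size of 0.8 with 25 per arm, two-sided 5%. By the normal approximation, power = Φ(d√(n/2) − 1.96) = Φ(0.8 × √12.5 − 1.96) = Φ(2.828 − 1.960) = Φ(0.868) = 0.807; a two-sample t calculation gives 0.791. The stated figure reproduces. The time of debriefing enters none of its inputs, and the documents give no size for the effect of disclosure, so no loss of power can be derived.

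**5. Could the trial data show the effect?** No. No group is defined by when it was debriefed, so any effect of disclosure in controls cannot be separated from that of the training.

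**The case against.** The strongest reply is that this is largely a silence. The Debriefing paragraph says after the instrument, without saying at once; the Potential risks paragraph sets a later earliest time; and a team guided by the stated rationale would wait. This stands in part: the plan permits early disclosure and does not mandate it. A reader might infer that controls will be told early, and the documents do not support that. Consent pages are also not in the text available, and the debriefing statement is not reproduced, so the absence of a rule can be asserted only for the text at hand.

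Second, controls are already cued. Screening asks about earlier bias training, consent mentions cognitive biases, the standardized caregivers are Black, and both arms complete the IAT and race-attitudes questionnaire before training. This stands, and it makes the added effect of a formal statement smaller. Being cued is still not the same as being told the aims outright.

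Third, the control is defined by the absence of mitigation techniques, which is not the same as unawareness of the topic. Telling both arms before encounter 2 could equalize awareness and isolate the techniques, whereas waiting leaves the active arm more aware and open to demand effects. This is a fair design argument, and the documents do not show which distortion is larger. Waiting is preferred because it follows the protocol's own rationale, and the unequal awareness should be stated as a limitation.

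**Conclusion.** The concern holds as a minor point. The two disclosure times are not reconciled for the two-encounter design, and neither protects encounter 2, so controls may learn the racial-bias focus before the primary endpoint is measured.

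The size of any consequence is unknown and may be small. Attenuation is a plausible direction for the between-arm contrast if controls are told early, but it rests on the protocol's own statement that knowledge of the focus alters communication, and no magnitude is given.

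A reader might also take the protocol's word about invalid results to mean that the Phase 2 comparison would be invalid. The documents do not support that. Allocation is randomized, so the comparison stays valid; what early disclosure changes is what the control condition consists of. The Analysis plan also describes a pilot whose primary goal is feasibility, which limits the consequence further.

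**What to change.** Amend the Potential risks and Debriefing paragraphs to give one Phase 2 rule: the debriefing statement is shown to both arms only after encounter 2, at the close of the same half-day session, subject to IRB approval. Note that the active arm meets the topic of bias during training by design.

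Keep the IAT immediately after encounter 1, so that it remains the baseline moderator for the planned interaction with treatment group.

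State two limitations: residual cueing of both arms by the IAT and race-attitudes questionnaire, and unequal topic awareness at encounter 2, with possible demand effects.

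The cost is a wording amendment and an IRB submission, with no extra staff, visits or participants. The downside is that incomplete disclosure lasts slightly longer, and the protocol names passive deception as a possible source of distress. The reminder about removing one's data also comes later in the half-day, although the right to discontinue is already explained at consent. The IRB should weigh this.
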